## **6.4 Study Period**

### **6.4.1 Cycle 1 Day 1**

Cycle 1 Day 1 procedures may be completed on the same day as Baseline procedures (see the Schedule of Activities, **Table 1**). The following assessments and procedures will be performed:

- Vital signs and body weight will be measured (see Section 7.3.3);
- ECOG PS (see [Appendix 1](#));
- Concomitant medication and AE data will be collected and reviewed.

Subjects will be given a diary to record study medication compliance details.

Subjects will be asked to bring back all used packs of study medication and the diary when they return for the next visit.

Subjects will be instructed to avoid extended unprotected exposure to sunlight (e.g., sunbathing) or tanning for the duration of the study period and end of treatment visit (approximately 4 weeks after completion of study drug).

### **6.4.2 Cycle 1 Day 15 ( $\pm 2$ days)**

Subjects will attend the clinic on Cycle 1 Day 15 ( $\pm 2$  days) for the following assessments:

- Vital signs and body weight will be measured (see Section 7.3.3);
- Concomitant medication and AE data will be collected and reviewed.

### **6.4.3 Day 1 of Subsequent Cycles (-4/+2 days)**

Subjects will visit the investigator site on Day 1 (-4/+2 days) of each subsequent cycle for the following assessments:

- Vital signs and body weight will be measured (see Section 7.3.3);
- ECOG PS (see [Appendix 1](#));
- Blood samples will be collected (hematology, blood chemistry, see Section 7.3.3). Safety laboratory tests may be done up to 72 hours prior to the visit;
- Concomitant medication and AE data will be collected and reviewed;

After the end of Cycle 1, follow the study schedule as outlined in Table 1:

- Tumor assessments will occur after the end of Cycle 1 then follow the study schedule as outlined in Table 1. The assessment may be performed up to 7 days prior to the visit to facilitate availability of results to the investigator at the time of the clinic visit.

### **6.4.4 Imaging**

A CT scan of the tumor area will be conducted at the end of Cycle 1 (within 7 days of the start of subsequent cycle including Day 1 of subsequent cycle). The scan is to include the chest and other applicable sites of disease, determined by the investigator.

### **6.4.5 End of Treatment Visit**

If a subject comes off treatment for complete surgical treatment, intolerance to study treatment, or subject withdrawal, etc., they should return to the study site as soon as possible for assessments of efficacy and safety as follows (see Schedule of Activities Table 1).

- Vital signs and body weight will be measured (see Section 7.3.3);
- ECOG PS (see Appendix 1);

- Blood and urine samples will be collected (hematology, blood chemistry, coagulation, pregnancy test [if required], urinalysis; see Section 7.3.2). Safety laboratory tests may be done up to 72 hours prior to the visit;
- Concomitant medications and AE data collection and review;
- If tumor assessments have not been done within the last 4 weeks for patients who discontinue treatment for reasons other than disease progression, these will be obtained as soon as feasible;

#### **6.4.6 Post Treatment Follow-up Visit**

At least 28 days, and no more than 35 days, after discontinuation of treatment, subjects will return to the study site and the following assessments will be performed (see Schedule of Activities Table 1).

In case subjects continue on therapy after complete surgical treatment, assessments of safety and survival status at post treatment follow-up visit should be performed at least 28 days, and no more than 35 days after end of treatment visit assessments.

- Vital signs and body weight will be measured (see [Section 7.3.4](#));
- Subsequent cancer therapy;
- Concomitant medications and AE data collection and review.

Subjects continuing to experience treatment-related toxicity at this point after discontinuation of treatment will continue to be followed at least every 4 weeks until resolution or determination, in the clinical judgment of the investigator, that no further improvement is expected.

#### **6.4.7 Follow-up**

Subjects should be followed up until 1 month after surgical treatment. Telephone contact or other means to obtain timely regular follow-up is recommended. The

information for subsequent therapies collected and recorded on the CRF should include drugs administered, date of initiation and discontinuation of each medication.

#### **6.4.8 Subject Withdrawal**

A subject may withdraw from treatment at any time at their own request, or they may be withdrawn at any time at the discretion of the investigator for safety, behavioral, or administrative reasons. Reasons for withdrawal include, but are not limited to the following:

- Progressive disease as defined by RECIST version 1.1 (as determined by investigator assessment) and judged by investigator that the patient no longer derives clinical benefit from study treatment;
- New systemic anticancer therapy instituted;
- Unacceptable toxicity;
- Global deterioration of health-related symptoms;
- Study non-compliance;
- Subject becomes pregnant;
- Subject withdraws from treatment;
- Lost to follow-up;
- Die;
- Study termination by investigator.

If subjects require more than 2 consecutive weeks of dose interruption, a discussion should be made with the investigator.

If a subject does not return for a scheduled visit, every effort should be made to contact the subject. The investigator should inquire about the reason for withdrawal, request that the subject return all unused investigational product(s), request the subject returns for a final visit if applicable, and follow up with the subject regarding any unresolved AEs.

If the subject withdraws from the study and also withdraws consent for disclosure of future information, no further evaluations should be performed and no additional data should be collected. The investigator may retain and continue to use any data collected before withdrawal of consent.

## **7. ASSESSMENTS**

Every effort should be made to ensure that the study required tests and procedures are completed as described. However, it is anticipated that from time to time there may be circumstances, outside of the control of the investigator that may make it unfeasible to perform the test. In these cases the investigator will take all steps necessary to ensure the safety and well-being of the subject. When a study required test cannot be performed, the investigator will document the reason and any corrective and preventive actions which he/she has taken to ensure that normal processes are adhered to as soon as possible.

### **7.1 Timing of Assessments**

All subjects being considered for the study must sign an informed consent within 28 days of start of treatment, and prior to any study specific screening procedures. Baseline assessments must be performed within 14 days prior to commencing study treatment, except pregnancy test (if applicable). Pregnancy test result needs to be known to be negative prior to study treatment. In case of serum sample, pregnancy test needs to be conducted within 72 hours prior to Cycle 1 Day 1. In case of urine sample, pregnancy test needs to be conducted on Cycle 1 Day 1 before study treatment is started.

On visits after Cycle 1 Day 1, laboratory assessments may be performed up to 72 hours and tumor/imaging assessments up to 7 days prior to Day 1 of any cycle in order for results to be available for investigator review at time of subject visit.

## **7.2 Efficacy Assessments**

### **7.2.1 Tumor Response Assessment**

Objective tumor response will be measured using RECIST v1.1 (see Appendix 3) and assessed by the investigator (INV).

Imaging tumor assessments at screening are to be performed within 28 days prior to commencing study treatment. All measurements should be recorded in metric notation using a ruler or calipers.

Investigators are encouraged to select greater than one lesion, representative and reproducible and to include the largest lesion, when identifying target lesions to be followed.

The same method and technique should be used to characterize each lesion identified and reported at Baseline, during the study treatment period, and during follow up.

### **7.2.2 Tumor Tissue**

Informed consent will be obtained prior to tissue acquisition and testing for each patient. After the last cycle of induction therapy, the tumor tissues will be collected immediately by surgical resection. Tumor and lymph node collection from definitive surgical resection and sampling of fresh tumor sample (as applicable dependent on the size of residual tumor) is mandatory on the day of surgery. Processing of the remainder of the specimens for histopathologic analysis should be performed within 72 hours of the procedure. Sections will be used for local pathology review assessing pCR and MPR.

Tumor tissue samples collected during the screening period and post-operation will be used for Whole Exome Sequencing (WES) to investigate the correlation between changes in tissue clonality and neoadjuvant therapy efficacy. Additionally, based on

tissue mutation results, a customized blood testing gene panel (PANEL) will be designed to enhance detection rates in blood samples. Residual specimens should be processed for histopathological analysis within 72 hours of collection. Sections will be reviewed by the local laboratory for pathological assessment to evaluate pCR and MPR.

### **7.2.3 Blood Sample Analysis for ctDNA (circulating tumor DNA)**

For patients meeting the inclusion criteria, blood samples (20 mL each) will be collected at baseline, 2 weeks, 4 weeks, and end of neoadjuvant therapy, pre-operation, 3 days and 1-month post-operation to provide specimens for biomarker analysis. These samples will be used for ctDNA analysis based on NGS platforms to evaluate the correlation between biomarkers with respond and outcomes.

## **7.3 Safety Assessments**

The following parameters will be assessed at time points detailed in **Table 1** Schedule of Activities:

- ECG;
- Safety laboratory data;
- ECOG PS (ref to [Appendix 1](#) is needed);
- Vital signs;
- AEs.

### **7.3.1 12 Lead ECG**

A 12-Lead ECG will be performed at screening and baseline with a 10 second rhythm strip. If the subject experiences signs or symptoms of a cardiac or neurologic

disorder (specifically syncope, dizziness, seizures, or stroke), ECG should be obtained at the time of the event.

To ensure safety, if there is finding of QTc >500 msec, the ECG must be repeated. If there is finding of QTc >500 msec again (i.e.,  $\geq$ CTCAE Grade 3), the ECG must be reviewed by qualified personnel at the site as soon as the finding is made, including verifying that the machine reading is accurate and that the Fridericia's or Bazett's correction formula is applied.

An electronic reading of prolonged QTc must be confirmed by a manual reading. Before concluding that an episode of QTc prolongation is due to study drug, thorough consideration should be given to potential precipitating factors (e.g., a change in the subject's clinical condition, the effect of concurrent medication, electrolyte disturbance) and a possible evaluation by a specialist. If the QTc reverts to  $\leq$ 500 msec, and it is the opinion of the investigator that the prolongation was not due to the study drug, treatment may be continued with regular ECG monitoring.

### **7.3.2 Safety Laboratory Data**

Safety laboratory studies may be done up to 72 hours prior to the point indicated on the Schedule of Activities (Table 1) on any cycle, to facilitate availability of results to the investigator at the time of the clinic visit.

**Table 5: Laboratory Evaluations**

Screening for Eligibility		
Hematology	Blood Chemistry	Other
Hemoglobin	AST (SGOT)	Urinalysis (blood, protein, glucose, by dipstick; microscopic examination of sediment if abnormalities on urine dipstick)
Platelet count	ALT (SGPT)	
WBC count	Creatinine	
Absolute neutrophil count	Total bilirubin	Calculation of the creatinine clearance determined by the Cockcroft-Gault formula or site's standard formula.
Absolute lymphocyte count		
Absolute monocyte count		Pregnancy Test (urine or serum)

Baseline and during the Treatment Period		
Hematology	Blood Chemistry	Other
Hemoglobin	Alkaline phosphatase	Pregnancy test (urine or serum) at baseline.
Platelet count	AST, ALT	In case of serum sample, pregnancy test needs to be conducted within 72 hours prior to Cycle 1 Day 1. In case of urine sample, pregnancy test needs to be conducted on Cycle 1 Day 1 before study treatment is started. Pregnancy test (urine or serum) at end of treatment if mandated by institutional policy or at the discretion of the investigator.
WBC count	Total bilirubin	
Absolute neutrophil count	Calcium (total or ionized)	
Absolute lymphocyte count	Magnesium	
Absolute monocyte count	Potassium	
	Sodium	
	BUN or urea	
	Albumin	

### 7.3.3 Vital Signs

Vital signs include pulse rate, sitting or supine blood pressure, respiratory rate and body temperature.

The information will be recorded in the subject's medical records and if clinically significant, data will be recorded as an AE in the CRF.

## 8. ADVERSE EVENT REPORTING

All observed or volunteered AEs regardless of treatment group or suspected causal relationship to the investigational product(s) will be reported as described in the following sections.

For all AEs, the investigator must pursue and obtain adequate information both to determine the outcome of the AE and to assess whether it meets the criteria for classification as a SAE requiring immediate notification by drug label. For all AEs, sufficient information should be obtained by the investigator to determine the causality of the AE. The investigator is required to assess causality. Follow-up by the investigator may be required until the event or its sequelae resolve or stabilize at a level acceptable to the investigator.

As part of ongoing safety reviews conducted by the investigator any non-serious AE that is determined by the investigator to be serious will be reported as an SAE. To assist in the determination of case seriousness further information may be requested from the investigator to provide clarity and understanding of the event in the context of the clinical study.

## **8.1 Reporting Period**

For SAEs, the active reporting period to the investigator or its designated representative begins from the time that the subject provides informed consent, which is obtained prior to the subject's participation in the study, i.e., prior to undergoing any study-related procedures and/or receiving investigational product, through and including 28 calendar days after the last administration of the investigational product regardless of the start of any subsequent cancer therapy. SAE should be reported via the CRF in the active reporting period. Following the active safety reporting period, other SAEs of which the investigator becomes aware should be reported to drug provider, unless the SAE is attributed by the investigator to complications of either the underlying malignancy or any subsequent anti-cancer therapy or to the patient's participation in a subsequent clinical study.

Non-serious adverse events should be recorded on the CRF from the time the subject has taken at least one dose of study treatment through last subject visit.

If a subject begins a new anticancer therapy, the AE reporting period for non-serious AEs ends at the time the new treatment is started.

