Lorlatinib will be administered orally QD at approximately the same time of the day on a continuous daily dosing schedule, ie, without a break in dosing in the absence of drug-related toxicity. Patients must swallow the study medication whole and must not manipulate or chew the medication prior to swallowing. Patients should be instructed to take their medication at approximately the same time every day. A dosing card will be provided to the patients to provide guidance for the correct use of lorlatinib. Patients must be instructed that should they miss a dose or vomit any time after taking a dose, they must not “make it up” with an extra dose. Instead, resume the subsequent doses as originally prescribed. Any missed dose may be taken up to 6 hours prior to the next scheduled dose, otherwise it should be skipped and dosing resumed with subsequent doses as prescribed. The patient must be instructed to record all doses (including missed or vomited) in a dosing diary supplied by the site. If doses are missed or vomited, this must be indicated in the source documents and Case Record Forms (CRFs).

The response to neoadjuvant therapy will be evaluated by the investigators utilizing RECIST 1.1 criteria. Patients demonstrating no progressive disease as per these criteria will proceed to surgical resection with radical intent, scheduled within 6 weeks following the conclusion of lorlatinib neoadjuvant therapy. Patients completing the surgical intervention and pathological evaluation will conclude their participation in this study within 1-month post-surgery and may continue to receive subsequent treatment as deemed appropriate by their healthcare providers, based on prevailing clinical practice.

This study will intermittently collect blood specimens from patients at baseline, during neoadjuvant therapy, and perioperatively to explore changes in tumor biomarkers. Baseline and postoperative tissue specimens will be obtained, and Whole Exome Sequencing (WES) will be performed to investigate the correlation between neoadjuvant therapy efficacy and tissue mutation changes. Additionally, tissue

mutation results will be used to customize a blood testing panel to enhance detection rates.

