Informed consent will be obtained from all participants prior to study enrollment. The consent process will ensure that patients are fully aware of the study's nature, its objectives, the investigational therapy involved, and the potential risks and benefits of participation. The study emphasizes rigorous adherence to ethical standards and patient safety, with a comprehensive plan in place for monitoring adverse events and implementing dose adjustments as necessary to manage toxicity.

Subjects will be on therapy until complete surgery and pathological evaluation, withdrawal of consent, death, or investigator decision dictated by protocol compliance, whichever occurs first. At the time of termination of study treatment, the patients could continue to receive treatment according to clinicians' decision in their clinical practice.

This study will take 18 months to enroll subjects, and each subject will be followed up for efficacy and safety during neoadjuvant process and 1-month post-surgery. Dose reduction information for management of AEs is included in Section 5.

Safety and efficacy assessments were performed throughout the treatment period and at the end-of-study visit. Routine safety assessments included the collection and evaluation of AEs, concomitant medications, vital signs, and body weight. Particular attention was given to AEs consistent with the lorlatinib toxicity profile (including lipid elevation, cognitive and mood disorder, etc.). Additional safety assessments performed at selected visits included ECOG PS, clinical laboratory tests, ECGs.

Safety assessments and efficacy assessments will be performed throughout the study as described in the Schedule of Activities (Table 1).

Study Activity	Screening & baseline ≤28 days of start of treatment	Cycle 1 Week 1-4	Cycle 2 Week 5-8	End of neoadjuvant (pre-surgery assessment)	End of treatment visit (Surgery complete)	Final follow-up visit (1 month after surgery)
Visits		Day 1	Day -4±2 day			
Informed consent 	X					
Medical history and demographics 	X					
ALK+ status	X					
Physical examination	X					
ECOG PS 	X	X	X	X	X	X
Brain scan MRI or CT 	X					
Vital signs  , Body weight, Height 	X	X	X	X	X	X
ECG 	X	X	X	X		X
Laboratory 						
Hematology 	X	X	X	X	X	X
Blood chemistry 	X	X	X	X	X	X
Urinalysis 	X	X	X	X	X	X
Pregnancy test 	X				(X)	

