13. Adverse event assessment includes tumor-related, treatment-related and unrelated signs and symptoms. The reporting period for non-serious AEs starts from the time the subject has taken the first dose of study treatment and ends at last subject visit or upon initiation of a subsequent anticancer treatment, whichever occurs first. The reporting period for serious AEs starts once a subject provides informed consent and ends 28 days after the last dose of study treatment irrespective of the start of

any subsequent anticancer treatment. Subjects must be followed for AEs at Post-Treatment Follow-up Visit at least 28 (and no more than 35) days after the end of treatment, or until all drug-related toxicities have resolved or are deemed irreversible, whichever is later. The National Cancer Institute Common Terminology Criteria for Adverse Events, Version 5.0 (CTCAE v5.0) will be used to grade AE severity.

14. Tumor assessments will include: PET/CT, or through computed tomography (CT), abdominal ultrasound, cranial MRI/CT, and bone scintigraphy at screening, in order to determine the accurate TNM staging. Physical examination for peripheral adenopathy or skin/subcutaneous nodules representing target measurable (by caliper) disease, if any are present.. Imaging serves also as safety assessment to monitor/exclude pulmonary toxicity. Chest X-ray will be performed on the first postoperative day to assess the surgical outcome and any procedural events. A chest X-ray will be conducted one month postoperatively to evaluate postoperative pulmonary recovery, including the presence of pleural effusion.
15. Subject Status Follow-up for Survival: Repeat tumor assessments are suggested to be done approximately every 4 weeks from the date of CT/MRI at the end of study treatment. Telephone contact approximately every cycle from post treatment follow-up visit to obtain regular follow-up is recommended. The information collected for subsequent therapies should include enumeration of the post-study treatment, including drugs administered, and date of initiation and discontinuation of each drug; and will be recorded in the CRF.

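### The only stated CRF period for serious adverse events ends 28 days after the last lorlatinib dose and can close before, or soon after, the operation the trial leads up to

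*Protocol*

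**What the plan says.** - **SAE period.** Section 8.1 starts active SAE reporting at consent and continues it "through and including 28 calendar days after the last administration of the investigational product". Footnote 13 to the Schedule of Activities (Table 1, in section 3.1) agrees: the period "ends 28 days after the last dose of study treatment".
- **CRF entry.** Section 8.1 links the CRF to that period: "SAE should be reported via the CRF in the active reporting period". For the time afterwards it says: "Following the active safety reporting period, other SAEs of which the investigator becomes aware should be reported to drug provider". It exempts events attributed to the malignancy, to subsequent anticancer therapy or to a later study.
- **Non-serious AEs.** Section 8.1 records these once the subject has "taken at least one dose of study treatment through last subject visit". Footnote 13 says the period "ends at last subject visit or upon initiation of a subsequent anticancer treatment, whichever occurs first".
- **Surgery and follow-up.** Section 5.1 ends dosing on completion of 6-8 weeks of neoadjuvant treatment. Section 3.1 then has surgery "scheduled within 6 weeks following the conclusion of lorlatinib neoadjuvant therapy" and states that "each subject will be followed up for efficacy and safety during neoadjuvant process and 1-month post-surgery". Section 6.4.7 and the last column of Table 1 also put the end of follow-up at 1 month after surgery.
- **Use of the data.** Safety and tolerability is a secondary endpoint (section 2.2), and section 9.3 summarises it for every dosed subject.

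**The concern.** The SAE period is counted from the last dose, while safety follow-up is counted from the operation. Since up to 6 weeks may separate the two, the stated SAE period can close before the patient reaches the operating theatre.

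The rule also works the wrong way round. After day 28, a minor postoperative event still has an explicit CRF period, up to the last visit or the start of new anticancer therapy, but a serious one does not. Section 8.5 makes any AE that prolongs a hospital stay serious, so the postoperative events of most interest come under the shorter rule.

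A site that applies the end date in section 8.1 may leave later SAEs off the CRF. A site guided by section 8.11, or by the AE marks in Table 1, may enter them. The section 9.3 summaries could then under-count serious postoperative events relative to non-serious ones, and six sites contributing 25 patients could be working to different rules.

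**Working it through.** The protocol states no figure for this overlap, so there is none to reproduce. The check is day arithmetic from the last dose (day 0).

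**Inputs**
- End of the SAE period: day 28 (section 8.1; Table 1 footnote 13).
- Surgery on day *s*, with 0 ≤ *s* ≤ 42, which gives 43 permitted dates (section 3.1, 6 weeks).
- Final visit on day *s* + *m*, where *m* is the length of 1 month (sections 3.1 and 6.4.7). The protocol does not give *m* in days. I assume 30 and show 28 and 31 as the range.

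**Postoperative days outside the SAE period**

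The postoperative days are *s* + 1 to *s* + *m*, so

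uncovered = min(*m*, max(0, *s* + *m* − 28)).

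| Surgery on day *s* | Final visit (*m* = 30) | Uncovered, *m* = 30 | *m* = 28 | *m* = 31 |
|---|---|---|---|---|
| 0 | day 30 | 0 + 30 − 28 = 2 | 0 | 3 |
| 7 | day 37 | 7 + 30 − 28 = 9 | 7 | 10 |
| 14 | day 44 | 14 + 30 − 28 = 16 | 14 | 17 |
| 21 | day 51 | 21 + 30 − 28 = 23 | 21 | 24 |
| 28 | day 58 | 28 + 30 − 28 = 30 (all) | 28 (all) | 31 (all) |
| 42 | day 72 | 30 (all; capped at *m*) | 28 (all) | 31 (all) |

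For surgery on day 42 the SAE period closes 72 − 28 = 44 days before the final visit (42 to 45 days over the range of *m*). Of those 44 days, 30 are postoperative; the other 14 are days 29 to 42, which include the operation itself.

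**First postoperative week (days *s* + 1 to *s* + 7)**
- Fully inside if *s* + 7 ≤ 28, that is *s* = 0 to 21: 22 dates.
- Partly inside for *s* = 22 to 27: 6 dates.
- Wholly outside for *s* = 28 to 42: 15 dates.

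22 + 6 + 15 = 43, and 15/43 = 0.349, or 35% of the permitted dates. This is a share of calendar dates. It is not a share of patients and not a rate of missed events.

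**Does any other text set a later SAE period on the CRF?**
- Section 8 covers all observed or volunteered AEs, but refers to the sections that follow for how they are reported. The first of these is 8.1.
- Sections 8.10 and 8.11 ask for AEs to be reported, 8.11 on the CRF. Neither gives a period.
- Section 8.7 requires the causal relationship of procedure-related SAEs to be recorded on the CRF. It gives no period and does not say whether the study resection counts as a study procedure.
- Table 1 marks AEs at the surgery-complete and final visits, but that row carries footnote 13, which ends SAEs at day 28.

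None of these moves the limit. Equally, section 8.1 nowhere says that later SAEs must stay off the CRF.

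**The case against.** The best counter-argument is that this is a set of imperfectly aligned clocks, not a true cut-off.

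- Footnote 13 goes on to require AE follow-up at a visit 28-35 days after the end of treatment, or until drug-related toxicity settles if that is later. Table 1 labels the end-of-treatment visit as completed surgery, and section 3.1 describes subjects as on therapy until surgery and pathology are done. Read that way, AE follow-up extends about a month beyond surgery. Section 6.4.6 uses a similar count for subjects who continue therapy after surgery.
- Section 8 has any event later judged serious reported as an SAE, with no end date. Section 8.4 requires SAE recording of a fatal outcome of the malignancy during the study.
- Later SAEs are not lost to safety oversight. The investigator will learn of many at the scheduled visits, and section 8.1 still sends them to the drug provider.
- Section 9.3 sets no data cut-off, and section 7.2.2 has tissue taken at resection straight after the last cycle, which points to early surgery and a gap of only a few days.

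Much of this is fair. It shows that the protocol is ambiguous and that notification continues after day 28. It does not supply a later CRF period: both SAE rules count from the last dose, however the end of treatment is read, and the section 8.4 provision covers only death from the malignancy. The drug-provider route depends on the investigator becoming aware, has attribution exceptions, and mentions no CRF entry. Early surgery would shrink the gap, but 42 days remain permitted.

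**Conclusion.** The point holds and should be fixed. The only stated CRF period for SAEs stops short of the planned safety follow-up, and the protocol leaves open which rule governs afterwards. With a 30-day month the shortfall runs from 2 of 30 postoperative days (surgery on day 0) to all 30 (surgery on day 28 or later). With a 28-day month there is no shortfall for surgery on day 0.

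The size in practice depends on when patients are operated on, which the protocol does not say. Under-counting of serious postoperative events in the section 9.3 summaries is therefore a possibility and has not been demonstrated. The primary endpoint and its two-stage decision rule are unaffected, and no effect on the separately defined surgical complication rate has been shown.

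**What to change.** In section 8.1 and in Table 1 footnote 13, end the active, CRF-based SAE period at the later of 28 days after the last lorlatinib dose and the final visit 1 month after surgery, and state that these SAEs enter the section 9.3 summaries. A patient who never reaches surgery keeps the 28-day end. With a 30-day month the period would end between day 30 (surgery on day 0) and day 72 (surgery on day 42; 70 to 73 over the range of *m*), leaving no uncovered days for surgery within the 6-week window.

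Optionally, say in section 8.7 that the study resection is a study procedure for reporting purposes. While editing, check that the end-of-treatment wording in sections 3.1, 5.1 and 6.4.6 and in footnote 13 agrees with the new period.

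The cost is one sentence in each of the two places and a few extra SAE forms. No visit is added, since Table 1 already collects AEs at the surgery-complete and final visits.
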